### **9.6.4. Safety Analysis**

Patient incidence rates of all AEs will be tabulated by Medical Dictionary for Regulatory Activities (MedDRA) system organ class (SOC), and by MedDRA preferred term (PT). Narratives of deaths, all discontinuations, serious AEs, pregnancies and AEs of special interest (AESI) will also be provided.

All treatment emergent AEs, all treatment emergent AEs potentially related to TEGSEDI, all treatment emergent serious AEs, and all treatment emergent serious AEs potentially related to TEGSEDI will be summarized.

Incidence (95% confidence interval) of AEs occurring within 1 day of TEGSEDI administration, and time to onset from TEGSEDI injection and duration of these AEs will be summarized by visit and overall in any visit. The rates of AEs during the 1-day visit occurring after preventive measures will also be summarized. Resolution time with and without treatment administered for the AEs will be summarized.

For each study visit on treatment, the result and change from pre-dose baseline in vital signs (body temperature, heart rate, respiratory rate, and systolic, diastolic blood pressure) and cytokines/inflammatory markers will be summarized using descriptive statistics for all patients in the Evaluable Set and by presence/absence of AEs within 1 day of TEGSEDI administration.

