#### ***11.4.3.5. Outcome of the Adverse Event***

If the event is a non-serious AE, then the event's outcome is characterized by one of the following:

- **AE Persists:** Patient terminates from the trial and the AE continues
- **Recovered:** Patient recovered completely from the AE
- **Became Serious:** The event became serious (the date that the event became serious should be recorded as the Resolution Date of that AE and the Onset Date of the corresponding SAE)
- **Change in Severity (if applicable):** AE severity changed

If the event is an SAE, then the event's outcome is characterized by one of the following:

- **Ongoing:** SAE continuing
- **Persists (as non-serious AE):** Patient has not fully recovered but the event no longer meets serious criteria and should be captured as an AE on the non-serious AE eCRF (the SAE resolution date should be entered as the date of onset of that AE)
- **Recovered:** Patient recovered completely from the SAE (the date of recovery should be entered as the SAE resolution date)
- **Recovered with Sequelae:** The signs/symptoms of the reported SAE have improved but not completely resolved, and a new baseline for the patient is established since full recovery is not expected
- **Fatal:** Patient died (the date of death should be entered as the SAE resolution date)
- **Unknown:** The outcome of the reported SAE is not available, e.g., patient is lost to follow-up

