#### ***11.4.3.6. Follow-up of Adverse Event***

##### **Investigator Follow-Up**

During the study period, the investigator should follow each AE until the event has resolved to baseline grade or better, the event is assessed as stable, the patient is lost to follow-up, or the patient withdraws consent. Every effort should be made to follow all SAEs, AESIs, considered to be related to TEGSEDI or related to study procedures until a final outcome can be reported.

Resolution of AE (with dates) should be documented on the AE eCRF and in the patient's medical record.

The investigator should follow up or support the Sponsor's effort to follow up with all pregnancies reported during the study from either the study patient or the female partner of male study patient until pregnancy outcome is available. If the pregnancy results in the birth of a child, the mother and infant may continue to be followed for up to 8 weeks after birth.

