### 8.2.2.2 Adverse Events Occurring Within 24 hours of TEGSEDI Administration

AEs occurring within 24 hours of administration of TEGSEDI are defined as all AEs with an onset date/time no longer than the 24-hour planned timepoint using a window interval from 20 to 30 hours after the date/time of the injection. For AEs with missing time of onset, AEs occurring within 24 hours of TEGSEDI administration are defined as AEs with an onset date of the same day as the TEGSEDI administration or the subsequent day. This rule will also be applied for missing time of administration of TEGSEDI.

The incidence of AEs occurring within 24 hours post TEGSEDI administration will be summarized at each visit and overall using counts and percentages in the evaluable set. The incidence will be reported with 95% confidence intervals (CIs). Additionally, a summary of AEs occurring within 24 hours post TEGSEDI administration will be displayed by SOC and PT and will be summarized at each visit and overall.

The denominator for the calculation of the percentages by visit will be the number of patients who received a TEGSEDI administration for the specific visit. The denominator for the calculation of the percentages for the overall occurrence of AEs in any visit will be the number of patients in the evaluable set. These denominators will also be presented in the table.

The time from the injection of TEGSEDI until the occurrence of the first AE will be summarized by each visit and overall using descriptive statistics for continuous variables. The time (hours) will be calculated as:

(Onset date/time of the AE – injection date/time of TEGSEDI)/3600

Time from injection of TEGSEDI until the onset of the AE will only be summarized for the AEs with available time for the onset of the AE and available time of TEGSEDI injection. Where time is not available, the AE will be included in the incidence count but will not be included in the summary of time to onset.

The duration of AEs occurring within 24 hours of TEGSEDI administration (in hours) will be calculated as:

- $(\text{Date/time of resolution} - \text{date/time of onset})/3600$

Duration of the AEs will only be calculated for AEs with an outcome of "Recovered" or "Recovered with sequelae" for which date/time for onset and resolution is available.

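### SAP 8.2.2.2 drops recovered AEs that have a resolution date but no clock time; where such times are missing, the duration summary is likely to be biased short

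*Combined protocol and SAP*

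**What the plan says.** Protocol 9.6.4 makes duration a planned output: "time to onset from TEGSEDI injection and duration of these AEs will be summarized by visit and overall in any visit". It also plans resolution time with and without treatment.

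SAP 8.2.2.2 defines duration in hours, as date/time of resolution minus date/time of onset. It limits the calculation to outcomes of recovered or recovered with sequelae, and within those to AEs "for which date/time for onset and resolution is available". Under its heading on treatment and duration, the SAP repeats the calculation separately for AEs with and without treatment given.

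The same section allows for missing clock times elsewhere. If the onset or injection time is missing, calendar dates decide whether the AE counts as within 24 hours. Such an AE stays in the incidence count but "will not be included in the summary of time to onset". There is no rule for an AE with a resolution date and no resolution time, beyond its exclusion.

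On what sites record, protocol v2.0 section 11.4.3.6 says: "Resolution of AE (with dates) should be documented on the AE eCRF and in the patient's medical record". For a recovered SAE, section 11.4.3.5 says "the date of recovery should be entered as the SAE resolution date". Neither mentions a time of day.

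**The concern.** The exclusion is unlikely to be random with respect to duration. Patients are assessed at 1, 2, 4 and 8 hours and again at 20-30 hours (protocol 9.1.2); the next scheduled on-treatment visit is four months later (9.1.1). An AE that ends by the return visit can readily be given a clock time. One that ends later must be timed from the patient's account, and a date is easier to obtain than an hour. If times are missing, they are therefore most likely missing for the longer AEs.

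The study exists to characterise post-injection AEs. A rule that keeps short AEs and loses long ones makes reactions look briefer than they are, which is the unfavourable direction for a safety study. The split by treatment given inherits the loss: if treated and untreated AEs differ in true duration, the contrast shrinks.

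**Working it through.** **No stated figure to reproduce.** The documents give no expected duration, no onset distribution and no rate of missing times. The size below rests on assumptions.

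**Assumptions.** Onset is exponential with mean 6 h, capped at 24 h. The return visit is uniform over 20-30 h (the window is from the protocol). Duration is log-normal with log-SD 1 and true median 6, 12, 24 or 48 h. Every AE that ends by the return visit has a clock time; of those that end later, a share *q* has one. All AEs recover.

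**Formula.** Let *p* be the share ending by the return visit, *E* their mean duration, and *M* the true mean, which is median × e^0.5. Later-resolving AEs contribute *M* − *pE* to the mean. The SAP rule then reports

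mean(*q*) = [*pE* + *q*(*M* − *pE*)] / [*p* + *q*(1 − *p*)].

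**Worked case, true median 24 h.** Simulation gives *p* = 0.40 and *E* = 11.3 h; *M* = 24 × 1.649 = 39.6 h. So *pE* = 4.52 and *M* − *pE* = 35.08.

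- *q* = 0: 11.3 h, and 11.3/39.6 = 0.285, so 71% low.
- *q* = 0.5: (4.52 + 17.54)/(0.40 + 0.30) = 31.5 h, 20% low.
- *q* = 0.75: (4.52 + 26.31)/(0.40 + 0.45) = 36.3 h, 8% low.
- *q* = 0.9: (4.52 + 31.57)/(0.40 + 0.54) = 38.4 h, 3% low.
- *q* = 1: 39.6 h, no bias.

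**All four medians** (how far the reported mean is low, from unrounded inputs):

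| True median | True mean | Share ending by return visit | q = 0 | q = 0.5 | q = 0.75 | q = 0.9 |
|---|---|---|---|---|---|---|
| 6 h | 9.9 h | 84% | 35% | 16% | 8% | 3% |
| 12 h | 19.8 h | 65% | 55% | 21% | 10% | 4% |
| 24 h | 39.6 h | 40% | 71% | 20% | 8% | 3% |
| 48 h | 79.1 h | 18% | 83% | 13% | 5% | 2% |

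The reported median is 16-72% low at *q* = 0 and 8-28% low at *q* = 0.5.

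**Effect on the treatment split, worst case.** With exponential durations, onset uniform over 0-8 h, last contact at 24 h and no later times, a true median of 12 h is reported as 7.2 h and one of 48 h as 9.3 h. A fourfold contrast becomes 9.3/7.2 = 1.3.

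**Check of the remedy.** In the first model, suppose every later-resolving AE has a date only and injections are between 08:00 and 12:00 (assumed). Giving those AEs the midpoint of the interval their dates allow brings the mean to within about 1% of the truth and the median to within 9%.

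**The case against.** The strongest reply is that the documents do not show that resolution times go uncollected. The date wording is in protocol v2.0, while SAP section 2 says it serves v3.0 of 23 May 2023, and the eCRF is not shown. Section 11 of v2.0 also speaks only of an onset date, yet the protocol plans time to onset from injection. Its wording may be generic, with the eCRF setting the fields, and the SAP formula presupposes that some resolution times exist. A recalled time entered on the form would satisfy the rule and be kept. Investigators must follow each AE until it resolves or is stable, and patients are also monitored under the product label, so contact does not stop for four months. The shortfall would be partly visible, because continuous summaries report n (SAP section 8) and all AEs are listed. Incidence is unaffected.

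Most of this stands, and it rules out a stronger reading: that later-resolving AEs do drop out and reported durations are cut to roughly one day. That follows only if no later-resolving AE has a time, which no passage says. Nor does it follow from date-only recording, which would leave no AE with a duration in hours and empty the summary altogether.

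It does not remove the point. Follow-up to resolution helps secure a date more than an hour, and an AE with only a date is what the rule discards. A smaller n shows that AEs are absent, not that the absent ones tend to be longer. No count of date-only AEs is specified in the SAP text.

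**Conclusion.** The point holds in conditional form. It is certain that SAP 8.2.2.2 excludes recovered AEs with a resolution date but no time, and that the supplied protocol text asks only for dates. How many AEs this affects is unknown. If any are affected, the direction is predictable: durations too short, overall and in the split by treatment given.

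Under the stated log-normal model the mean is 35-83% low in the worst case, 13-21% low if half of later-resolving AEs have a time, 5-10% low at three quarters, 2-4% low at nine tenths, and unbiased with full capture. These are illustrations across an assumed range, not estimates for this trial.

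The separate restriction to recovered outcomes is not what is at issue: the AEs lost here have resolved, so censoring unresolved AEs would not bring them back. The change is worth making before the final analysis because it is cheap, and it does no harm if times prove complete.

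**What to change.** In SAP 8.2.2.2, replace the complete date/time condition so that every recovered AE with onset and resolution dates enters the duration analysis:

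- Where both times exist, calculate hours as now.
- Otherwise, take the shortest and longest durations the dates allow, never starting before a known onset time. Use the midpoint in the main summary, and repeat the summary with all shortest and then all longest values as a sensitivity analysis.
- Add a table of duration categories that dates can support, for example up to 24 h, over 1 to 3 days, over 3 to 7 days and over 7 days. Give two columns of counts, one from the shortest and one from the longest values, so that AEs crossing a boundary are visible.
- Report the number of AEs with date only and the number excluded, overall and by treatment given yes/no.
- State in the SAP which onset and resolution fields the eCRF holds.

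The cost is SAP wording and a small derivation, with no new data. The drawback is precision. With a known onset time and a date-only resolution, the interval is at most 24 h wide and the midpoint is off by at most 12 h. With both ends date-only, the error can reach a day.

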### Preventive Measures Used Prior to the TEGSEDI Injection

The incidence of AEs occurring within 24 hours will also be calculated for injections with preventive measures as reported by the eCRF question "Did the patient take any preventive measures prior to the administration of the dose". The incidence of AEs will be calculated for TEGSEDI administrations with and without preventive measures by visit and overall for any visit. The denominator for the calculation of the percentages by visit will be the number of patients who received a TEGSEDI administration with or without preventive measures, respectively. For the calculation of the overall occurrence of AEs with or without preventive measures, the patients will be included in the denominator if the patient received at least one TEGSEDI administration with or without preventive measures, respectively.

The preventive measures as reported on the Dosing at Visit eCRF will be provided as listings.

### Treatment and Duration of AEs within 24 hours

Duration of the AEs will be calculated separately for AEs where treatment was given to mitigate and where treatment was not given. Whether or not treatment was given will be taken from the AE page in the eCRF (Question Treatment given Yes/No).

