##### 11.4.3.2. Severity

The severity of AEs and SAEs will be graded as follows:

- **Mild:** The event is easily tolerated by the patient and does not affect the patient's usual daily activities
- **Moderate:** The event causes the patient more discomfort and interrupts the patient's usual daily activities
- **Severe:** The event is incapacitating and causes considerable interference with the patient's usual daily activities

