#### ***11.4.3.4. Treatment Given for Adverse Event***

Any treatment (e.g., medications or procedures) given for the AE should be recorded on the AE eCRF. Treatment should also be recorded on the concomitant treatment or ancillary procedures eCRF, as appropriate.

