## 8 Statistical Methods

For this phase IV study, only descriptive analyses will be provided. No hypothesis testing will be done. However, 95% confidence intervals will be provided where indicated using the Clopper-Pearson method. Descriptive statistics will comprise the number of observations (n), mean, standard deviation (SD), standard error (SE) of mean, median, minimum, and maximum for continuous variables, and n and percent for categorical variables.

The overall study baseline is defined as the last available observation prior to the first on study TEGSEDI administration.

For each study visit on treatment, changes in vital signs and cytokines/inflammatory markers post-injection of TEGSEDI are calculated relative to the pre-injection values, not relative to the overall baseline values. For visit level summarization, analyses will be performed by the study visit using data as collected in the electronic case report form (eCRF).

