## 8.2.2 Adverse Events

### 8.2.2.1 Treatment-emergent Adverse Events (TEAEs)

TEAEs are defined as AEs with an onset date/time on or after the date/time of the first on study administration of TEGSEDI. Related TEAEs are TEAEs with a reported relationship of "Possible" or "Related". TEAEs with a missing relationship will also be counted as Related. Serious Adverse Events (SAEs) will be indicated as such in the eCRF and can be defined as treatment emergent, based on when the SAE initiated. AEs will be summarized using the safety set for the treatment period among both patients who develop a hypersensitivity reaction and those patients who do not develop a hypersensitivity reaction.

TEAEs will be summarized as follows:

- Overview of Treatment-emergent AEs
- Treatment-emergent AEs by System Organ Class and Preferred Term
- Treatment-emergent AEs by System Organ Class, Preferred Term and Severity
- Treatment-emergent AEs Related to TEGSEDI by System Organ Class and Preferred Term
- Treatment-emergent AEs Related to TEGSEDI by System Organ Class, Preferred Term and Severity
- Treatment-emergent Adverse Events of Special Interest (AESI) by System Organ Class and Preferred Term

 	
Title: Statistical Analysis Plan
 
Program Name: "A Phase 4 Safety Study Assessing the Adverse Events Occurring Within 24 Hours of TEGSEDI Administration in Patients with polyneuropathy of Hereditary Transthyretin-mediated Amyloidosis (hATTR-PN)"
 
Protocol #: TEG4004
 
[REDACTED]
 
Version: Final 2.0 Effective Date: 06 October 2023

--	---

- Treatment-emergent AESIs by System Organ Class, Preferred Term and Severity
- Treatment-emergent Serious AEs by System Organ Class and Preferred Term
- Treatment-emergent Serious AEs Related to TEGSEDI by System Organ Class and Preferred Term
- Treatment-emergent AEs leading to discontinuation of TEGSEDI by System Organ Class and Preferred Term

AEs will also be presented in data listings as follows:

- Listing of All Adverse Events
- Listing of Adverse Events Leading to Discontinuation
- Listing of Serious Adverse Events
- Listing of Adverse Events of Special Interest

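### Duration of 24-hour AEs is summarised by treatment given or not, with no account of severity, so the crude split can make treatment look unhelpful or mask a benefit

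*Combined protocol and SAP*

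**What the plan says.** The SAP paragraph on treatment and duration, within section 8.2.2.2, reads: "Duration of the AEs will be calculated separately for AEs where treatment was given to mitigate and where treatment was not given". The treated or untreated label comes from a single yes/no item on the AE page of the eCRF. Protocol 9.6.4 plans the same summary: "Resolution time with and without treatment administered for the AEs will be summarized". The protocol abstract repeats it. None of these places mentions severity or type of AE.

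Three other provisions bear on the point.

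- **Severity is available.** Protocol 11.4.3.2 says "The severity of AEs and SAEs will be graded as follows" and lists mild, moderate and severe. Protocol 11.3.3 requires severity to be assessed for each AE on the eCRF. The SAP uses it only in incidence tables, such as "Treatment-emergent AEs by System Organ Class, Preferred Term and Severity", with similar tables for related TEAEs and AESIs.
- **Treatment of an AE is recorded, not assigned.** Protocol 11.4.3.4: "Any treatment (e.g., medications or procedures) given for the AE should be recorded on the AE eCRF". That section states no rule for who is treated.
- **Not every AE gets a duration.** Duration is resolution minus onset, and SAP 8.2.2.2 adds: "Duration of the AEs will only be calculated for AEs with an outcome of" recovered or recovered with sequelae, with both date/times available.

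SAP section 8 sets the frame: "For this phase IV study, only descriptive analyses will be provided". It plans no hypothesis tests.

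**The concern.** Severity in protocol 11.4.3.2 rests on how well the event is tolerated and how far it disrupts daily activities. Both could plausibly drive a decision to treat. If more severe AEs also last longer, the treated group holds more of the long AEs, and its mean or median duration is higher even when treatment does nothing. A real shortening could be hidden for the same reason.

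A second mechanism works in the same direction: an AE that lasts longer offers more time in which someone may treat it. For a treated AE, the measured duration also includes the interval before treatment, which treatment cannot shorten.

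Treatment required is part of the stated objective in both documents, and this split is the main analysis the SAP describes for it. Readers will tend to take the two columns as evidence on whether treating these reactions helps. The SAP does not warn against that, and protocol 9.8 covers selection and survivor bias but not this.

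**Working it through.** **Stated figure.** The documents give no figure for the duration analysis. Their only sizing statement (75 patients, a 4% AE, 95% probability) reproduces as 1 − 0.96^75 = 0.953, but it does not bear on this point.

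**Inputs.** The split variable, the duration definition and the severity scale come from the documents. The severity mix, durations and treatment probabilities below are all assumptions.

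**Formula.** For severity grade *s* with share *w*, mean duration *d* and probability of treatment *p*:

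- treated mean = Σ(w·p·d) / Σ(w·p)
- untreated mean = Σ(w·(1−p)·d) / Σ(w·(1−p))

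With no treatment effect, the ratio within each grade is d/d = 1.00 by construction.

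**Three grades,** mix 60/30/10% mild/moderate/severe. The last column supposes that treatment truly shortens every treated AE by 30%, so the correct ratio there is 0.70.

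| Durations (h) | P(treated) | Treated mean (h) | Untreated mean (h) | Ratio, no effect | Ratio, 30% shorter |
|---|---|---|---|---|---|
| 6/12/24 | 0.2/0.4/0.6 | 12.0 | 8.6 | 1.40 | 0.98 |
| 6/12/24 | 0.1/0.4/0.8 | 14.3 | 7.9 | 1.80 | 1.26 |
| 6/24/72 | 0.2/0.4/0.6 | 26.4 | 14.4 | 1.83 | 1.28 |
| 6/24/72 | 0.1/0.4/0.8 | 34.6 | 12.2 | 2.85 | 1.99 |
| 6/24/72 | 0.3 in all | 18.0 | 18.0 | 1.00 | 0.70 |
| 12 in all | 0.1/0.4/0.8 | 12.0 | 12.0 | 1.00 | 0.70 |

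The means shown are those with no effect. First row in full: treated (0.12×6 + 0.12×12 + 0.06×24)/0.30 = 3.6/0.30 = 12.0 h; untreated (0.48×6 + 0.18×12 + 0.04×24)/0.70 = 6.0/0.70 = 8.6 h.

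In the last two rows one of the two dependences is absent, and the crude ratio is then correct.

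**Two grades,** 70% milder at 24 h and 30% worse at 72 h:

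- Treated in 20% and 80%, no effect: (0.14×24 + 0.24×72)/0.38 = 54.3 h against (0.56×24 + 0.06×72)/0.62 = 28.6 h, ratio 1.9.
- Same, but treatment halves duration: 54.3/2 = 27.2 h against 28.6 h, ratio 0.95 where the truth is 0.50.
- Treated in 30% and 60%, no effect: (0.21×24 + 0.18×72)/0.39 = 46.2 h against (0.49×24 + 0.12×72)/0.61 = 33.4 h, ratio 1.4.

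**Effect of the outcome rule.** Under protocol 11.4.3.5 a non-serious AE may end as persisting, having become serious, or changed in severity; none of these gets a duration under the SAP. Suppose that removes some severe AEs from the 2.85 scenario:

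- half removed: 27.8 h against 11.3 h, ratio 2.45
- all removed: 18.0 h against 10.5 h, ratio 1.71

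The distortion shrinks but remains, because moderate AEs still differ from mild ones.

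**The case against.** The strongest reply is that nothing is being estimated. The SAP calculates two summaries and plans no difference, ratio or test. The objective is to characterise AEs, including what treatment was required, which is not a question about whether treatment worked. How long treated AEs last, and how long untreated ones last, are each useful facts and each is correct as computed. This stands. A reader might infer that the plan contains a biased estimate of a treatment effect; the documents do not support that. The harm arises only if the two columns are read causally.

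Second, the magnitudes are assumed. The severity definitions concern disruption of daily activities, not duration; a short severe reaction or a long mild one fits them. This also stands. A reader might infer that the table will make treatment look harmful; the documents show only that it could, and the outcome rule makes the size less certain still.

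Third, severity strata are an incomplete remedy. They do not deal with type of AE, or with longer AEs having more time to be treated, and with about 75 patients some cells will be small. That is a reason for a footnote beside the strata, not for leaving severity out.

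Last, the mock tables in SAP Appendix B are not in the supplied text and might show severity. The SAP text does not call for it.

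**Conclusion.** The point holds as a minor weakness in a descriptive summary. The duration split ignores severity, which is already collected, and carries no caution on how to read it. If both treatment and duration rise with severity, the crude treated/untreated ratio under no true effect is about 1.4 to 2.85 in the scenarios examined, against 1.00 within severity grade. With a true 30% shortening (correct ratio 0.70), the three-grade scenarios with both dependences show 0.98 to 1.99. If either dependence is absent there is no distortion from this source, and the outcome rule may reduce it. These figures illustrate the mechanism; they do not predict this trial's results.

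**What to change.** In SAP 8.2.2.2, under treatment and duration:

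1. Present duration for treated and untreated AEs within severity grade: mild, moderate and severe, with moderate and severe pooled if sparse.
2. For each of the two groups, show the severity mix and the number of AEs left out of the duration calculation.
3. Add a footnote that treatment was not assigned, that longer AEs have more time in which to be treated, and that the split does not estimate a treatment effect.

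A row giving time from first treatment to resolution may look like a natural addition, but it is better left out. It removes pre-treatment time from the treated group alone while untreated AEs are still counted from onset, and so would tilt the table in favour of treatment.

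The change needs SAP wording and a few table rows, with no new data. The downside is small counts within grade; where they are too small to summarise, the severity mix and the footnote still serve the reader.
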